5.3. Procedures

Positron Emission Tomography (PET): Regional and global myocardial blood flow will be assessed using PET imaging. Clinical and research cardiac PET studies are routinely performed at BWH. The PET imaging team at BWH under [name] leadership consist of experienced imaging specialists and have a track record in research studies using PET. [name] has extensive experience in performing these procedures, quantifying myocardial blood flow and flow reserve, has published extensively on this topic, and runs an active core laboratory with experience in multi-center trials using imaging endpoints. PET scans will be performed using a whole-body PET/CT scanner. Study participants will be asked to refrain from drinking caffeine-containing beverages and taking theophylline-containing medications for 12 hours before the PET study. Calcium channel blockers, beta blockers, and arterial vasodilators will be withheld for 24 hours prior to the PET scan. Studies will be performed after 4 hours of fasting.

Assessment of myocardial blood flow and CFR: Regional myocardial blood flow (MBF) will be measured at rest and during vasodilator-stress with adenosine using ^{13}N -ammonia or $^{82}\text{Rubidium}$ as the flow tracer. ^{13}N -ammonia and $^{82}\text{Rubidium}$ is used in clinical and research studies and has been validated for the quantification of myocardial blood flow and CFR. After transmission imaging and beginning with the intravenous bolus administration of ^{13}N -ammonia (~5 mCi) or $^{82}\text{Rubidium}$ (15-20 mCi), list mode images will be acquired for 6-10 minutes. The patient will then undergo a standard infusion of adenosine (140 mcg/kg/min) for 4 mins or regadenoson bolus injection (0.4 mg). Two mins into the adenosine infusion or one minute after the regadenoson bolus, a second dose of ^{13}N -ammonia (~20 mCi) or $^{82}\text{Rubidium}$ (15-20 mCi) will be administered, and PET imaging collected in the same manner. Heart rate, blood pressure, and 12-lead electrocardiogram will be recorded at baseline, every minute during the infusion, and during 5 minutes after completion of the adenosine infusion or regadenoson injection. The calcium score (CAC) CT is acquired in axial mode with 120 kVp, 90 mAs, 32x0.625 mm collimation with approximately 5 s acquisition time, and still falls within the 1–2 mSv radiation dose approved for this study. All CT images were reconstructed with 2.5 mm thickness. CAC is scored using the Agatston method.

Analysis of PET data: Absolute MBF (in ml/g/min) will be computed from the dynamic rest and stress images using commercially available software (Corridor4DM; Ann Arbor, Michigan) and previously validated methods^{52,53}. Automated factor analysis will be used to generate blood pool (arterial input function) and tissue time-activity curves. Regional and global rest and vasodilator-stress MBF will be calculated by fitting the ^{13}N -ammonia or $^{82}\text{Rubidium}$ time-activity curves to a two-compartment tracer kinetic model as described previously^{52,53}. Per-patient global CFR will be calculated as the ratio of MBF at peak vasodilator-stress over that at rest for the entire left ventricle. This method for quantitation of MBF

is highly reproducible. In the PET core laboratory at BWH, the intra-class correlation coefficient for CFR among four readers is 0.94 (95%CI 0.88-0.98), indicating excellent reproducibility²⁴.

Echocardiographic Images

Quantitative analysis of echocardiograms: All echocardiograms will be analyzed by cardiologists blinded to randomized treatment assignment. LV volumes will be determined by the modified Simpson's method in the apical 4 and 2 chamber views, and LVEF will be calculated from volumes in the standard manner.⁶⁹ Peak early mitral annular relaxation velocity (E') will be measured from both the septal and lateral aspects of the mitral annulus. Mitral flow velocity will be assessed by pulsed wave Doppler from the apical 4-chamber view by positioning the sample volume at the tip of the mitral leaflets. The deceleration time of the E wave is measured as the interval from the peak E wave to its extrapolation to the baseline⁷⁰. LV mass will be calculated by the ASE recommended formula for estimation of LV mass from LV linear dimensions and indexed to body surface area, and relative wall thickness (RWT) will similarly be calculated as recommended by ASE guidelines⁶⁹. LA volume will be assessed by the biplane area-length method from apical 2- and 4-chamber views at end-systole from the frame preceding mitral valve opening and indexed to body surface area (LA volume index, LAVi). In our laboratory, the intra-class correlation for E' is 0.98 (CV 5.8%), indicating excellent reproducibility.

Assessment of LV Strain: B-mode speckle-tracking analysis will be performed off-line using validated vendor-independent software (Cardiac Performance Analysis, Tomtec system, Munich, Germany),⁷¹ which has demonstrated excellent reproducibility in our laboratory⁷²⁻⁷⁵. The endocardial border is traced at an end-diastolic frame in apical 4- and 2- chamber views and at an end-systolic frame in short axis view, where end-diastole is defined by the QRS complex or the frame just before mitral valve opening. Adequate tracking of speckles along the endocardial and epicardial borders throughout the cardiac cycle is visually assessed. Peak longitudinal, radial and circumferential strain and strain rate curves are then computed automatically and provided as global and segmental data including 6 segments in each view⁷⁶. In our laboratory, the intra-class correlation for peak global longitudinal strain (GLS) is 0.87 (CV 8.0%), indicating excellent reproducibility

Coordination of ancillary study and central imaging analyses. BWH will serve as the coordinating center and central imaging core laboratory for the proposed PET scans in the pilot study. [name] runs a very active core laboratory and, as mentioned above, has extensive experience in managing multi-site imaging trials. For the central analysis of the PET images, all imaging data will be stripped of patient identifiers and assigned a trial-specific identifier to maintain compliance with US regulatory requirements regarding protection of patient privacy. Drs. [name] and [name] will organize a bi-monthly teleconference including investigators and research coordinators from each clinical site to monitor, discuss, and troubleshoot recruitment and other issues that may arise during the conduct of the clinical trial.

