3. SPECIFIC AIMS

3.1 Hypothesis and Objectives

The central hypothesis of this study is that reducing systemic inflammation using Tildrakizumab will quantitatively improve myocardial blood flow and CFR as measured by PET over six months in patients with moderate-to-severe psoriasis. In doing so, improvement in coronary vasoreactivity, endothelial function, and tissue perfusion may have beneficial effects on myocardial mechanics, left ventricular deformation and function and, ultimately, symptoms and prognosis. Accordingly, the following specific aims are proposed:

Aim 1. To test the hypothesis that systemic inflammation is a critical determinant of CFR and myocardial tissue perfusion, as assessed by quantitative PET imaging, in patients with moderate-to-severe psoriasis. Specifically, we propose that treatment with Tildrakizumab at a target dose of 100mg SC for 6 months will result in:

Hypothesis #1: Improved global CFR in response to adenosine, reflecting coronary vasodilator function, as compared to baseline.

Aim 2. To test the hypothesis that Tildrakizumab at a target dose of 100mg SC over 6 months will result in improved left ventricular (LV) myocardial mechanics, as assessed by transthoracic echocardiography, and that this functional improvement will be correlated with the change in CFR after 6 months of treatment. In this population of patients with moderate-severe psoriasis and at heightened cardiovascular risk, we propose to test the following hypotheses:

Hypothesis #2: Tildrakizumab for 6 months will result in improved LV systolic function, as assessed by measures of LV peak global longitudinal strain, and diastolic function, as assessed by measures of tissue Doppler mitral annular early diastolic relaxation velocity (E').

Hypothesis #3 Changes in LV systolic and diastolic function after 6 months of Tildrakizumab therapy will be correlated with changes in CFR.

3.2 Primary Endpoint:

Change (from baseline) in global CFR, as measured by PET imaging at 24 weeks after initiation of Tildrakizumab therapy.

3.3 Secondary Endpoints:

[figure not shown]
- 3.3.1. Correlation between the change (from baseline) in global CFR and psoriasis skin severity scores (Body surface area [BSA], Physician's Global Assessment [PGA], Psoriasis Area and Severity Index [PASI]) at 24 weeks after initiation of Tildrakizumab;
- 3.3.2. Change (from baseline) in peak-stress global myocardial blood flow (in mL/min/g) at 24 weeks after initiation of Tildrakizumab;

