- 3.3.3. Change (from baseline) in peak-stress global coronary vascular resistance (in mm Hg/mL/min/g) at 24 weeks after initiation of Tildrakizumab
- 3.3.4. Change (from baseline) in LV peak global longitudinal strain (GLS) and E' at 24 weeks after initiation of Tildrakizumab
- 3.3.5. Correlation of the change (from baseline) in LV peak GLS and E' with the global CFR at 24 weeks after initiation of Tildrakizumab

- 3.3.6. Change in serum biomarkers of inflammation (hs-CRP), myocyte injury and strain (hs Troponin, NT-proBNP) at baseline and 24 weeks after initiation of Tildrakizumab.
- 3.3.7 If the primary endpoint is positive, secondary exploratory analyses will use stored aliquots of plasma and serum to IL-6, TNFRII, ICAM, Glyc-A, p-selectin, e-selectin, sCD40L, adiponectin, and MCP-1.

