3. SUBJECT SELECTION

3.1. Study Design

Open label, single-center, single arm pilot study. Patients with moderate-to-severe psoriasis and evidence of cardiovascular risk factors will be recruited from Skin and Related Musculoskeletal Diseases Clinic and the Rheumatology Clinic from the Brigham and Women's Hospital. After giving written informed consent to participate in the study and fulfilling criteria for inclusion, patients will be scheduled for baseline cardiac PET/CT, echocardiogram and dermatology visit. On the day of the cardiovascular testing, patients will undergo rest and vasodilator-stress PET/CT scan for measurement of CFR at baseline), and again after completion of 24 weeks of therapy as well as echocardiogram. Labs will be drawn at the baseline visit and at the 24-week final cardiovascular visit. The baseline and follow-up cardiovascular visits will be scheduled within +/- 7 days of the Dermatology clinic visits for feasibility to allow patient and departmental coordination. Patients will be encouraged to remain on stable medical therapy throughout the enrollment period.

3.2. Study group:

In order to target a higher-risk population, we will enroll patients with evidence of moderate-to-severe psoriasis, which is the most closely linked to increased cardiovascular risk^{13,64,65}. We plan to target patients at heightened cardiovascular risk and coronary microvasculature dysfunction. In order to maintain feasibility, inclusion criteria will include *at least one* of the following: presence of DM, metabolic syndrome, or elevated hsCRP>mg/dl. We chose to use the cut-off of hsCRP \geq 2mg/dl which has been used as a cut point in large-scale clinical trials, including the CANTOS trial. CANTOS was the first trial in cardiology to show that in patients with a history of MI and elevated hsCRP \geq 2mg/dl, treatment with

canakinumab resulted in a reduction in recurrent cardiovascular events compared to placebo^{66,67}. Similarly, metabolic syndrome and DM are both well-known cardiovascular risk factors and studies from our research group have demonstrated reductions in CFR. Reduced CFR, which reflects coronary microvascular dysfunction, was further shown to be associated with major adverse cardiovascular events (MACE) across the spectrum of metabolic disease⁶⁸.

3.2.1. Inclusion criteria:

- Moderate-to-severe psoriasis
- Ages 18-90

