4.3. Treatment assignment

Study subjects will receive a total of three doses of 100mg of SC Tildrakizumab. Each dose will occur on weeks 0, 4 and 16, respectively.

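### The echo reader-blinding rule conceals a randomized assignment that this single-arm trial does not have, and no text provides for masking the GLS and E' reads to visit

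*Combined protocol and SAP*

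**What the plan says.** Section 5.3 (Procedures, Echocardiographic Images) contains the only reader-blinding statement in the document: "All echocardiograms will be analyzed by cardiologists blinded to randomized treatment assignment".

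The design sections describe a trial to which this cannot apply. Section 3.1 (Study Design): "Open label, single-center, single arm pilot study". Section 4.3 (Treatment assignment): "Study subjects will receive a total of three doses of 100mg of SC Tildrakizumab".

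The echo endpoint is a within-patient change. Section 3.3.4 lists "Change (from baseline) in LV peak global longitudinal strain (GLS) and E' at 24 weeks after initiation of Tildrakizumab", and Section 6.3 repeats it. The expected direction is set out in Section 3.1 (Hypothesis and Objectives), Hypothesis #2: "Tildrakizumab for 6 months will result in improved LV systolic function, as assessed by measures of LV peak global longitudinal strain", with E' named alongside as the diastolic measure.

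On the strain read, Section 5.3 says "B-mode speckle-tracking analysis will be performed off-line using validated vendor-independent software". It then says "The endocardial border is traced at an end-diastolic frame in apical 4- and 2- chamber views" and "Adequate tracking of speckles along the endocardial and epicardial borders throughout the cardiac cycle is visually assessed". The strain curves are computed automatically after that. The same section reports in-house reproducibility: ICC 0.98 (CV 5.8%) for E' and ICC 0.87 (CV 8.0%) for GLS.

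For PET, Section 5.3 describes automated generation of the input and tissue curves and a four-reader ICC for CFR of 0.94. It also says that identifying data are removed and a trial identifier assigned before central analysis, with privacy compliance as the stated reason. It does not mention visit, scan date or reading order.

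**The concern.** A blinding rule is useful only if it hides the contrast under test. Here that contrast is week 24 against baseline in the same patient. Every patient is untreated at the first scan and treated at the second, so a reader who knows the visit knows the treatment status. The written rule hides something else, which does not exist in this trial.

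In a randomized trial, a tendency to read later scans more favourably would affect both arms and largely cancel. In a single-arm trial nothing cancels it, and any shift common to the week-24 reads goes straight into the estimated mean change. GLS has two steps where a reader's judgement enters, and the hoped-for direction is known to everyone. A reader of the protocol would also take the sentence as assurance of a protection that it cannot give.

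**Working it through.** **Step 1: set the texts side by side.**

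- What the rule hides: randomized assignment (Section 5.3).
- What could be assigned: nothing. There is one arm (Section 3.1, Study Design) and one regimen for all (Section 4.3).
- What the echo endpoints contrast: baseline and week 24 (Sections 3.3.4 and 6.3).
- What would hide that contrast: masking to visit and scan date, with the order of reading randomized. No section provides for this, for echo or for PET.

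The rule and the contrast therefore do not meet. This conclusion needs no arithmetic.

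**Step 2: rank the exposure of the imaging measures.**

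- GLS: borders are traced and tracking is accepted by eye before the automatic computation; ICC 0.87, CV 8.0%. Most exposed.
- E': no comparable judgement step is described; ICC 0.98, CV 5.8%. Less exposed.
- CFR: largely automated; ICC 0.94 among four readers. Least exposed on the text.

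An ICC measures agreement between reads. It does not show that reads are free of a shift shared by all week-24 scans.

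**Step 3: illustrate how a paired test reacts to a shift.** The document gives no figure for reader bias and no SD of change for GLS or E'. Section 6.4 specifies a paired t-test for CFR only, so using it for the echo measures is an assumption, as is every shift below.

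First, a check of the method on the plan's own figure. For CFR, SD of change = 0.7 × √(2 × (1 − 0.7)) = 0.542. With a difference of 0.36 and a two-sided alpha of 0.05, the noncentral t gives 90.2% power at n = 26, which matches Table 2. That figure does not bear on masking.

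Now let the true effect be zero and let d be the systematic reading shift in units of the SD of change. The rejection probability is P(|t| > t(0.975, n − 1)) under a noncentral t with noncentrality d × √n. Take n = 35, or n = 35 × 0.8 = 28 if the 20% attrition comes out of the 35 (Section 6.1).

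| d (assumed) | n = 28 | n = 35 |
|---|---|---|
| 0 | 5.0% | 5.0% |
| 0.05 | 5.8% | 6.0% |
| 0.1 | 8.0% | 8.9% |
| 0.2 | 17.5% | 21.0% |

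The rate doubles to 10% at d = 0.128 (n = 28) or d = 0.113 (n = 35). These figures describe the test's sensitivity to a shift. They do not say how likely a shift is.

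**The case against.** The strongest reply is that this is a drafting slip. Appendix 2 also speaks of subjects being randomized, which suggests text carried over from another protocol, and the core laboratory may mask readers to visit as routine. That stands as far as it goes. A reader might infer that the scans will in fact be read unmasked, but the document does not support that. It shows only that no visit masking is provided for in writing. If masking is already practised, the remedy is to write it down.

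Second, reading quality is reported to be high and the strain curves are computed automatically. Both facts are fair and limit the concern, especially for E'. Neither excludes a systematic difference between visits, because tracing and acceptance come before the computation. A stated hypothesis is not evidence of biased reading either; it means only that the favourable direction is known.

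Third, a reader might infer that the primary endpoint is compromised in the same way. The text does not support that. The faulty sentence concerns echo alone, the CFR calculation is largely automated, and the document does not list what is removed from PET files, so whether visit or date survives cannot be known. For PET this is an omission of lower exposure.

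Fourth, the percentages could be taken as an estimate of the trial's error rate. They are not: both the shift and, for echo, the test are assumed.

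**Conclusion.** The point holds in this form: the stated echo safeguard cannot work in a single-arm trial, and no text provides for the masking that the baseline to week-24 comparison needs. The contradiction is certain on the text; the size of any resulting bias is unknown.

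The endpoints directly affected are secondary: change in GLS chiefly, and change in E' to a lesser degree. A constant shift would bias the mean change but leave the correlation of echo change with CFR as it is; only a shift that varied between patients could alter the correlation. The laboratory biomarkers are untouched. For CFR, visit masking should be stated too, as a side matter.

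Visit masking would remove this one source of bias. Regression to the mean, time trends and changes in co-treatment would remain, as in any uncontrolled before-and-after comparison. The sentence should be corrected because it promises something untrue and the correction is cheap, not because of the illustrative error rates.

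**What to change.** Replace the blinding sentence in Section 5.3 with:

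> Endpoint reads of echocardiograms (and of PET studies) will be done from coded files by readers masked to visit and scan date, with each patient's two studies read in random order once the week-24 study is available; baseline studies of patients without a week-24 study will be coded and read in the same masked batches. Clinical safety reads at the time of the scan are separate and are not used as endpoint values.

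The clause on patients without a week-24 study is needed because the plan expects about 20% attrition between the two PET scans, and those baseline scans would otherwise have no endpoint read.

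The cost is small:

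- Echo files need coding. A trial identifier is described for the PET files but not for echo.
- Baseline studies that had a prompt clinical look need a second, endpoint read. Section 9.1 calls for such a look at baseline PET, and Section 9.3 makes imaging findings a possible ground for discontinuation. The endpoint read is best done by an existing reader who did not do the clinical one, to limit recall.
- The masked PET reads of the first 20 patients must be complete before the interim conditional-power analysis of CFR (Section 6.1). The echo reads need not be.

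No extra scans, visits or patients are required.

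### Section 5.3 lets end-diastole for the strain tracing be the last frame before the mitral valve opens, a frame the same section elsewhere calls end-systole

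*Combined protocol and SAP*

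**What the plan says.** Three statements in section 5.3 bear on the point.

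- **Tracing frame, apical views** (Assessment of LV Strain): "The endocardial border is traced at an end-diastolic frame in apical 4- and 2- chamber views". For the short axis, the tracing is made "at an end-systolic frame in short axis view".
- **Definition of end-diastole** (same sentence): "end-diastole is defined by the QRS complex or the frame just before mitral valve opening". The strain paragraph gives no definition of end-systole.
- **Left atrial volume** (Quantitative analysis of echocardiograms): measured "at end-systole from the frame preceding mitral valve opening".

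After the tracing and a visual check of speckle tracking, the remaining step is automatic: "Peak longitudinal, radial and circumferential strain and strain rate curves are then computed automatically".

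The measurement feeds secondary endpoint 3.3.4, "Change (from baseline) in LV peak global longitudinal strain (GLS"), and the correlation endpoint 3.3.5. Both are repeated in section 6.3 as items 4 and 5. GLS is also the systolic measure in Hypothesis 2 of Aim 2, and it enters Hypothesis 3.

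**The concern.** A frame rule should pick out one moment in the cardiac cycle. This one offers two, and section 5.3 itself assigns the second to the other end of contraction. Choosing the frame and tracing the border is the main manual step before the software takes over, so it is where a wrong or shifting rule can enter the data.

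The design gives little protection. The study has a single arm, and the GLS endpoint is a within-patient change from baseline to week 24 in about 35 patients. If the frame were chosen differently at the two visits, the difference would enter the change score directly, with no control group in which the same reading difference would appear. Section 5.3 does not require the same frame rule at both visits.

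**Working it through.** The plan states no figure that depends on this rule, so the check is a comparison of text.

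**1. The two paragraphs side by side**

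| Place in section 5.3 | Frame | Phase assigned |
|---|---|---|
| Strain, first option | QRS complex | End-diastole |
| Strain, second option | Last frame before the mitral valve opens | End-diastole |
| Left atrial volume | Last frame before the mitral valve opens | End-systole |

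Rows two and three name the same frame and assign it opposite phases. They cannot both be right. If the left atrial paragraph is right, rows one and two are different moments, so the either/or in the strain paragraph does not offer two routes to one frame.

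**2. Whether anything else resolves it.** The strain paragraph refers to an end-systolic frame for the short axis but does not say how it is identified. No other section defines either phase.

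**3. Which endpoints are reached.** Longitudinal strain comes from the apical views, whose border is traced at the end-diastolic frame. The rule therefore reaches the GLS component of items 4 and 5 in section 6.3. E' is a mitral annular velocity and does not use the frame. CFR comes from PET. The power calculation in section 6.2 uses CFR only.

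**4. Size of the effect.** This cannot be derived from the documents. They give no GLS values and do not say that the traced frame fixes the zero-strain length. The following is an illustration on two assumptions that are not in the plan: strain = (L - L0)/L0, and the traced frame sets L0.

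Let the correct GLS, referenced to end-diastole, be -g. With the end-diastolic length set to 1, the end-systolic length is 1 - g. If the end-systolic length is used as L0, the reading becomes [1 - (1 - g)]/(1 - g) = g/(1 - g).

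| Assumed GLS | Calculation | Reading |
|---|---|---|
| -15% | 0.15/0.85 | +17.6% |
| -18% | 0.18/0.82 | +22.0% |
| -20% | 0.20/0.80 | +25.0% |

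The contradiction in steps 1 and 2 does not depend on this illustration.

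**The case against.** The strongest reply has four parts.

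- **The text speaks of tracing, not of reference length.** The border is drawn at the frame, speckles are followed through the whole cycle, and the software computes the curves. The short-axis border is traced at end-systole and strain is still derived automatically, which suggests that tracing frame and reference length may be separate. This stands. A reader might infer from the sentence that GLS will be calculated from an end-systolic reference and come out with the wrong sign. The documents do not say so, and the figures in the illustration must not be read as an expected error.
- **A sign reversal would be noticed.** Cardiologists read the studies, and a positive peak GLS would be conspicuous. This is fair for a gross error. It does not help with a smaller inconsistency between visits, and the only check described in the strain paragraph concerns the quality of tracking, not the choice of frame.
- **Readers will use the QRS complex.** It is listed first, and a reader who uses it is not misled. The laboratory also reports an intra-class correlation of 0.87 and a CV of 8.0% for GLS, which suggests a settled working method. Those figures describe the laboratory's record, however, and the plan does not say which frame rule produced them.
- **It is a drafting slip.** Very likely. A reader might go further and infer that opening was written for closure. That is one possibility. Another is that words defining end-systole were lost from the sentence, in which case the valve event is correct and its label is missing. The documents do not settle which.

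**Conclusion.** The concern holds as an internal contradiction in a stated measurement rule: wrong as written, minor severity. Section 5.3 gives the same frame two opposite labels, and the strain paragraph permits a reader to trace the apical border at a frame that the section elsewhere calls end-systole, or to use different frames at the two visits.

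Its reach is limited to the GLS parts of secondary endpoints 4 and 5. The primary CFR analysis, the sample size and E' are unaffected. A reader who uses the QRS option throughout makes no error. The numerical effect on GLS is unknown from the documents: the reading of about +22% for a GLS of -18% rests wholly on the assumption that the traced frame sets the zero-strain length.

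**What to change.** In the strain paragraph of section 5.3:

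1. Delete the mitral-valve-opening option for end-diastole and keep the QRS definition.
2. Define end-systole once, in line with the left atrial volume paragraph, so that the short-axis tracing has a stated frame.
3. Add that the same frame rule applies at baseline and week 24 for every patient.

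Deleting the option is safer than substituting another valve event, because the intended wording cannot be recovered from the documents. The cost is a sentence or two of protocol text. No patient procedure, visit or sample size changes. If any echocardiograms have already been read, confirm which frame was used and re-read those that do not follow the clarified rule.
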